a culturally adapted technology-delivered FBCO intervention for L/H families in rural Nebraska. Applying an iterative collaborative process, we will use a mixed-methods approach to culturally adapt FC to better fit the rural L/H community profile. A Community Workgroup facilitated by our rural partner organizations in Nebraska with a high population of L/H residents and theory-and data-driven approach using structured community input adaptation process will be conducted to develop and evaluate the relevance (ecological validity and equivalence), acceptability, and usability of all the adaptations made. We hypothesize that this process will lead to a program that is relevant, acceptable, and usable by L/H families in rural communities.

Aim 2: To evaluate the feasibility and preliminary effectiveness of a technology-delivered FBCO intervention for L/H families in rural Nebraska using RE-AIM and i-PARIHS. We will randomly assign participants to either FC (n=29) or an enhanced standard-care (SC) group (n=29) and determine overall study reach, preliminary effectiveness in reducing child BMI z-scores, potential for program adoption, implementation, and sustainability through local health departments (RE-AIM outcomes). SC participants will receive a workbook. FC participants will receive a workbook, 2 in person group sessions followed by 10 IVR calls over a period of 6 months. We hypothesize that a culturally adapted FC program will lead to a higher engagement (reach, retention and completion), significant higher proportion of L/H children reducing their BMIz scores at 6 months when compared to SC group, align (social validity) with health department perceptions of i-PARIHS constructs (Innovation, context, recipient characteristics), and that FC participants will view the intervention positively (i.e. relative advantage, observability, trialability, complexity, compatibility).

3. Background and Rationale

Describe the background of the study. Include a critical evaluation of existing knowledge, and specifically identify the information gaps that the project is intended to fill.

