Specific Aim 2: To evaluate the feasibility and preliminary effectiveness of a technology-delivered FBCO intervention for L/H families in rural Nebraska using RE-AIM and i-PARIHS. We will randomly assign participants to either the intervention or an enhanced standard care group (Figure 3). Sample Size Calculation. Sample size is based on the comparison of changes in BMI z-scores achieved by participants in FC-IVR with those achieved by participants in FC-workbook condition at 6 months post randomization²⁰. A total of 46 (23 per group) parent-child dyads achieves 80% power (alpha 0.05) to detect a significant difference between SC and IVR groups conditions. To account for a 25% attrition rate at 6-month we will recruit a total of 58 (29 per group) dyads. Participant Recruitment and Baseline Assessment Procedures. [name] will coordinate the recruitment of the participants with the help of CHWs. We will recruit a total of 58 dyads (Table 1). Baseline visits will take place at local community centers using private rooms. Dyads will complete informed consent, height, weight and waist circumference assessments, as well as complete a computer-based survey. Randomization will follow a random-numbers table (families/staff unblinded). Standard-Care. Families randomized to this group will receive FC-workbook. No additional materials or intervention contact will be provided. CHWs will follow a retention protocol to ensure these individuals return to 6-month assessments. Intervention Delivery. Families randomized to this group will receive the adapted version of the intervention described above. Drs. [name] and [name] will monitor IVR completion reports and assist the student-worker and CHWs in the on-going monitoring and engagement of participants during the intervention. Measurements and Data Collection. All measures (see table at PHS section for description) will be collected prior to intervention initiation and at 6 months post baseline (Figure 3). Weight will be assessed using a digital scale calibrated for accuracy prior to each assessment period using standard weights of a known quantity (e.g., 100-pound dumbbell). Height will be measured with a stadiometer, calibrated in 0.1-cm intervals. Waist circumference will be measured with a spring-loaded cloth tape measure at the level of the iliac crest using the average of the two closest measurements. Other Measures. Children and parents will complete measures of physical activity^{98,99}, eating behaviors¹⁰⁰, beverage intake¹⁰¹, quality of life^{102,103} acculturation^{104,105}, and health literacy¹⁰⁶. Parents will also complete home environment¹⁰⁷ surveys. During the 6-month assessment parents will complete program satisfaction surveys and a short exit interview with a CHW. Feasibility will be assessed according to intervention relevant factors (RE-AIM dimensions, engagement, attendance and completion rates), cost-effectiveness, cultural

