
relevance (aim 1 measures) and acceptability identified in exit survey/interviews to determine whether intervention is appropriate for further testing. Qualitative Analysis. Qualitative interviews and FGs will be recorded and transcribed in English or Spanish. The PI, with assistance from [name] and [name] will construct the interview codebook, with inductive codes added iteratively by in-depth reading of transcriptions until saturation is achieved. Transcripts will be double-coded in NVivo by [name], [name] and the PI. Inter-coder reliability using Cohens kappa (goal > 0.80) will be assessed. The research team has extensive experience conducting qualitative investigation^{20,22,26,51,58,62,67}, possesses local linguistic expertise (Drs. [name] and [name], speak Spanish), and will be aided by bilingual (English-Spanish) CHW staff. Statistical Analysis: The association of the intervention with the primary outcome of proportion of children reducing BMI z-scores will be tested using a chi-square test. The degree of association will be summarized using the odds ratio. If the assumptions of the chi-square test are violated, Fishers exact test will be utilized. Potential gender, and acculturation scores (external and familial language use, and social relations) differences will be explored via stratification. Comparisons between groups within gender will be done using Fishers exact test. Secondary aims outcomes include parent BMI, waist, PA, sweet beverages intake and eating behaviors, home environment changes and quality of life. The quantitative outcomes will be summarized using means and standard deviations or medians and inter-quartile ranges, as appropriate. If categorized, outcomes will be summarized using counts and percentages. Between group differences at 6-month will be capture using ANCOVA with the baseline measure as the covariate. If the ANCOVA assumptions are violated, a t-test (or if indicated, Wilcoxon's sum rank test) between group change scores (6-month baseline measure) will be used. Potential parental engagement (% of reach, retention and completion) and acculturation scores (language and media use, and social ethnic relations) differences will be explored via stratification. Comparisons between groups will be done using Fishers exact test. Significance level is 0.05.

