C. Are there any other financial obligations that the subject will incur as a result of participating in the study?

No

23. Compensation to the Subject for Participation

A. Will the subject receive any compensation for participation?

Yes

1. Describe the form of compensation, dollar amount (if applicable) and the prorated compensation plan (if applicable).

Participant will receive a \$25.00 gift card for completion of any focus group and \$25.00 for completion of usability test and \$25.00 for intervention assessments. To enhance retention, in addition to receiving full details on the results of their anthropometric measurements, both parents and child participants who complete each of the 3 study visits (0, 6 and 12 month) will receive a \$25.00 gift card each as a thank you for their time for a possible total of \$50.00

per family per visit - \$150 total over 12 months if they complete all 3 visits. CWG participants will be compensated for their involvement in this research study. A gift card of \$25 will be provided for each assessment (survey), meeting, and interview completed.

PRIOR REVIEW

24. Prior IRB Review

A. Has this study (or one substantially similar) been previously submitted to the UNMC IRB (or the Joint Pediatric IRB) and then withdrawn by the investigator for any reason?

Yes

1. Describe why the study was withdrawn.

Yes. Last year we got closer to the NIH funding line with our R21 proposal and requested an expedited review in order to respond to the JIT request that was granted a pending-funding IRB approval under the protocol 634-19-EP. Unfortunately, due budget cuts our project was not funded at that time and the IRB protocol was re-classified as withdrawn in January 28, 2020.

2. Describe changes made to the research plan prior to the current submission.

Minor changes were made after NIH review following reviewers recommendation, such as:

- Expand study area by increasing number of communities participants (from 1 to 4 partners health departments) with increased the number of focus groups participants for Aim 1.
- Aim 1 modification to include more detailed approach on procedures for intervention cultural adaptation.
- Changes on research team composition.

B. To the best of your knowledge, has this study (or one substantially similar) been considered by another IRB and disapproved?

No

SUBJECT IDENTIFICATION & RECRUITMENT

25. Method of Subject Identification and Recruitment

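### A retention procedure for the 6-month assessment is specified for standard-care families only, while retention is a hypothesised benefit of FC and the primary outcome needs that visit

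*Combined protocol and SAP*

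**What the plan says.** Section 12.B, Specific Aim 2, describes the two arms in consecutive paragraphs.

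- **Standard care.** Families receive the workbook. Then: "No additional materials or intervention contact will be provided". Then: "CHWs will follow a retention protocol to ensure these individuals return to 6-month assessments". In context, the individuals meant are the standard-care families.
- **FC.** Families receive the adapted program. Investigators review IVR completion reports and assist the student worker and "CHWs in the on-going monitoring and engagement of participants during the intervention". No procedure for securing the 6-month visit is stated.

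No other section extends the retention protocol to FC or says what it contains.

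Some retention measures are not tied to an arm. Section 23 gives gift cards to "both parents and child participants who complete each of the 3 study visits". Section 12.D lists monitoring of recruitment and retention as a research procedure. The Community Workgroup text in Section 12.B includes retention strategies among its meeting topics.

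Retention is also something the study wants to learn about. Section 2, Aim 2: "We hypothesize that a culturally adapted FC program will lead to a higher engagement (reach, retention and completion". The Statistical Analysis paragraph of Section 12.B lists "Potential parental engagement (% of reach, retention and completion) and acculturation scores" among the differences to be explored, and then names Fisher's exact test for comparisons between groups.

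The primary outcome in that paragraph is the proportion of children whose BMI z-score falls, tested by chi-square. The sample size text allows for 25% attrition, as a single rate for both arms. Section 12.E says that data will be examined for missing values, but gives no rule for a child without a 6-month measurement.

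**The concern.** Follow-up effort should be the same in both arms when return for assessment is itself of interest. If community health workers (CHWs) work to a return protocol in one arm and not the other, the observed retention rates reflect the program and the chasing together, and the data cannot separate them. A similar rate in both arms could mean that FC does not help retention, or that it helps and the standard-care protocol made up the difference. A higher rate in either arm would be just as hard to attribute.

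The second route is through missing data. The chi-square test uses a 6-month value, so whatever makes return differ by arm also decides which children contribute. If return is related to weight change, or if missing children are counted as not reduced, unequal return can create or mask a difference between arms. The trial is unblinded for families and staff, and Section IV says that CHWs will complete all in-person assessments. The people applying the protocol therefore know the allocation.

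**Working it through.** **1. The plan's own figure.** Inputs (Section 12.E, Sample Size Calculation): difference 0.05, SD 0.06, alpha 0.05, power 80%. Two-sided, normal approximation:

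n per arm = 2 × (1.960 + 0.842)² × (0.06/0.05)² = 22.6, rounded up to 23, so 46 in total.

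This matches the plan. The 58 recruited is 46 × 1.25 = 57.5, rounded up. (Dividing by 0.75 would give 62; that is a separate matter.) The calculation uses one attrition rate for both arms and does not address unequal return. Giving both arms the same procedure changes none of these numbers.

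**2. Retention comparison.** The documents give no arm-specific rates, so every rate from here on is an assumption. There are 29 families per arm.

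| Assumed attrition, standard care / FC | Retained, standard care vs FC | Fisher p |
|---|---|---|
| 25% / 25% | 22 vs 22 | 1.0 |
| 10% / 25% | 26 vs 22 | 0.30 |
| 10% / 40% | 26 vs 17 | 0.015 |

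In the other direction, suppose true retention is 90% with FC and 75% with standard care, and the protocol lifts standard care to 85%. Exact Fisher power, by enumerating all outcomes, falls from 0.200 to 0.028. The test is weak in either case. The example shows only that a follow-up effort in one arm can move this comparison.

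**3. Primary outcome with no true effect.** Let p be the proportion of children reducing BMI z-score, the same in both arms, with p assumed to be 0.50 to 0.60.

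*Missing counted as not reduced.* Shift (FC minus standard care) = p × (standard-care attrition − FC attrition).
- 10% / 25%: 0.50 × (−0.15) = −0.075; 0.60 × (−0.15) = −0.090.
- 10% / 40%: 0.50 × (−0.30) = −0.15; 0.60 × (−0.30) = −0.18.

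*Complete cases, with children who did not reduce twice as likely to be missing.* With attrition d, the chance of being missing among reducers is a = d / (p + 2(1 − p)), and the observed proportion is p(1 − a)/(1 − d).
- For p = 0.50: d = 0.10 gives 0.519, d = 0.25 gives 0.556 and d = 0.40 gives 0.611. The shifts are +0.037 (10% / 25%) and +0.093 (10% / 40%).
- For p = 0.60: the shifts are +0.038 and +0.095.

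*Complete cases, with missingness unrelated to outcome.* Shift about 0.

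Type I error of the chi-square test in a 20,000-run simulation at nominal 0.05:

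| Handling | 10% / 25% | 10% / 40% |
|---|---|---|
| Missing = not reduced | 0.09 to 0.10 | 0.21 to 0.27 |
| Complete case, related to outcome | about 0.06 | 0.09 to 0.10 |
| Complete case, unrelated | about 0.05 | about 0.05 |

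With 25% attrition in both arms the shift was about 0 throughout. Swapping the arms (25% standard care, 10% FC) reverses the signs.

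**4. Power for the mean difference** (noncentral t). This is 0.77 at 22 vs 22, 0.80 at 26 vs 22 and 0.74 at 26 vs 17. Unequal return is mainly a matter of bias and interpretation, not of power.

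**The case against.** The strongest reply is that the standard-care sentence is there to restore balance. FC families have two group sessions, ten calls and CHW engagement; standard-care families have a workbook and nothing else. A return protocol for the arm with no contact may narrow a gap that would otherwise favor FC. In that case it reduces differential missingness, and extending it to FC could even widen the gap again. This reading is plausible and cannot be excluded. But the plan does not state it as the purpose, does not describe the protocol, and does not provide for logging the effort, so nobody could later show that the two arms were chased equally.

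It is also fair that silence is not exclusion. The documents do not say that FC families get no return effort. The arm-neutral measures are real, and procedures are deferred to a manual that is not part of these documents. A reader might infer that all retention effort goes to standard care; the text does not support that.

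The Fisher sentence is ambiguous too. Engagement is to be explored by stratification, and reach is largely settled before randomization, so the list may not be meant wholly as an FC versus standard-care test. The words comparing with standard care in Aim 2 attach most directly to the BMI z-score clause. Retention is best described as a hypothesised FC benefit that will be explored, without a firmly specified test.

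Finally, the absence of a missing-data rule is a gap of its own, and an equal retention procedure does not close it.

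**Conclusion.** The point holds as a cheap improvement. As written, a procedure for securing the 6-month visit is specified for one arm and not for the other. That confounds any between-arm retention comparison and may produce differential missingness in the primary outcome.

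Two stronger conclusions are tempting and should not be drawn. A reader might infer that the standard-care protocol hides an FC advantage in retention. The documents do not fix the direction, because FC's additional contact may raise return in that arm while the protocol raises it in the other. A reader might also call the retention result uninterpretable. That goes too far: the incentive is common to both arms, dropout and its reasons are tracked (Table 1 in Section 12.E), and the comparison has little power at 29 per arm in any case.

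The size is equally open. The primary-outcome shifts run from about 0 to 18 percentage points in either direction. They depend on assumed arm-specific attrition, an assumed 50% to 60% of children reducing BMI z-score, and the handling of missing values, which the plan does not specify. They show sensitivity and are not estimates for this trial.

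**What to change.** In Section 12.B, move the retention sentence out of the Standard-Care paragraph and state that one 6-month assessment-retention procedure applies to both arms: the same reminders, number of contact attempts, incentives and make-up window. Record these contacts by arm, separately from IVR and group-session engagement contacts, so that return effort can be reported alongside retention. If both arms are already meant to receive the protocol, the sentence simply says so.

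The cost is a short text change and a few extra reminder contacts by the same CHWs to 29 FC families. The sample size, visit schedule and analysis are unchanged.

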Effectiveness	
 -Primary outcome (BMI z-score) and secondary clinical and self-management outcomes (Table 2) by control/IVR -Comparison of outcomes in subjects who withdraw vs. complete intervention - Staff and leaderships perceptions about delivering FBCO program via IVR and group sessions 	
 -Recruitment/enrollment/subject tracking logs (including completion, dropout and loss to follow-up rates/reasons) [CHWs] -Clinical data forms and surveys at 0,6 months [SW, CHWs] -Qualitative interviews with staff and leadership [[name] , PI [name]] 	
 Selected constructs will include: Facilitation: IVR and group based sessions and workbook facilitation strategies; Innovation: adaptation to deliver strategies to L/Hs in the context of rural NE
Adoption	
 - Staff and leaderships perceptions about delivering FBCO program via IVR and group sessions 	
 -Qualitative interviews with staff and leadership [[name] , PI [name]] 	Recipients : perceptions of participants (Beneficiaries), and staff (Recipients)
Implementation	
 - IVR completion reports; group session attendance and observation reports; proportion of content delivered as intended (fidelity) - Changes made during the implementation process (adaptation) tracked by the FRAME - Number of Calls completed and contact hours - Participant satisfaction - Qualitative feedback on barriers/facilitators from L/Hs/staff using i-PARIHS constructs 	
 -IVR completion forms (IVR System) [[name]] -IVR logged call duration (IVR System) [[name]] - Participant Satisfaction survey [SW, CHWs] -Qualitative interviews with participants, staff [[name] , PI [name]] 	Context : documentation of the capacity (human and financial resources); assessment of support from the leadership at the state and local levels

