Statistical Analysis: Descriptive, parametric, and non-parametric statistical methods will be used to compare continuous and categorical variables among the intervention groups at baseline. Data will be examined for the presence of outliers, violations of normality (for those continuous variables) and missing data. Major violations of normality will be corrected with an appropriate transformation procedure or non-parametric methods . Multi-level mixed effect models will be employed to control errors of non-independence, heteroskedasticity caused by parent-child dyad heterogeneity, and potential covariates to control to detect the BMI z-score reduction differences between the two conditions. In its simplest form, the model generally can be shown as:

$$BMIZscore_{it} = \mu + \alpha_i + X_{ijt} \beta + W_i \sigma + TT_t + \theta d_i + T_t + v_{it}$$

All measures are obtained for 3 time periods: baseline, 6, and 12 months. The dependent variable is BMIZ score for participant i at time point t . The unobserved participant-level heterogeneity that is not time dependent is represented by α_i , is allowed to vary by parent-child-dyads and to be a random variable. The X_{it} are time-period-level covariates and the W_i are participant-level covariates. The model also contains treatment group indicators d_i , and

time period indicators T_t . Relative treatment effect between conditions will be captured by coefficient θ and is the variable of interest. Sensitivity analysis will be conducted to examine the robustness of the mixed effect model across different random-effect distribution specifications (e.g., normal, finite mixture of normal etc.). Additional outcomes (e.g., parent BMI, waist circumference, PA, sweet beverages intake and eating behaviors, acculturation, home environment changes and quality of life) will be analyzed using ANCOVA with the baseline measure as the covariate. If the ANCOVA assumptions are violated, a t-test (or if indicated, Wilcoxon's sum rank test) between group change scores (6 or 12 month measure and baseline measure) will be used. Significance level for all tests is 0.05. Analyses will be performed using R 3.6 (R Core Team).

F. Does this study involve the collection of blood, urine, saliva or other human biological material (HBM)?

No

DRUGS, BIOLOGIC DRUGS AND DEVICES

13. Drugs and Biologic Drugs

1. Does this research involve the use of drugs or biologics?

No

14. Devices

1. Does this research involve a medical device(s)?

No

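### Sections 12.B and 12.E give different primary analyses of child BMI z-score, no rule says which governs, and the 80% power applies only to mean change

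*Combined protocol and SAP*

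**What the plan says.** **Section 12.B, Specific Aim 2, Statistical Analysis.** This section declares: "The association of the intervention with the primary outcome of proportion of children reducing BMI z-scores will be tested using a chi-square test". An odds ratio is the effect measure. There is a fallback: "If the assumptions of the chi-square test are violated, Fishers exact test will be utilized". The secondary outcomes listed there do not include child BMI z-score as a continuous measure.

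**Section 2, Aim 2.** The hypothesis expects a "significant higher proportion of L/H children reducing their BMIz scores at 6 months when compared to SC group". The objective refers only to "preliminary effectiveness in reducing child BMI z-scores", without saying whether that means a mean or a proportion. Neither sentence uses the word primary.

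**Section 12.E, Table 1, Effectiveness row.** "Primary outcome (BMI z-score) and secondary clinical and self-management outcomes".

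**Section 12.E, Statistical Analysis.** "Multi-level mixed effect models will be employed to control errors of non-independence". For the model itself: "The dependent variable is BMIZ score for participant" i at time t, with measurements at baseline, 6 and 12 months. The treatment coefficient "is the variable of interest. Sensitivity analysis will be conducted to examine the robustness of the mixed effect model". Parent BMI, waist circumference, physical activity and similar measures are placed under additional outcomes. No proportion of children is mentioned.

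**Sample size (sections 4.A.2, 12.B and 12.E).** All three statements rest on changes in BMI z-score. Sections 12.B and 12.E give 23 dyads per group for 80% power at alpha 0.05. Sections 4.A.2 and 12.E give the inputs: a difference of 0.05 and an SD of 0.06.

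**The concern.** The plan contains two candidate primary analyses of the same measurement. One reduces each child's change to yes or no and compares proportions at 6 months. The other models the score itself over three time points. Neither section carries the other's analysis, even as secondary, and both work at 0.05. On the same data one can be significant and the other not. Families and staff are unblinded, so leaving the choice until outcomes are known invites selective reporting, or the appearance of it.

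The power statement adds a second problem. It was derived for a comparison of means. If 12.B is followed, the 80% describes a different comparison from the test called primary and cannot be verified for that test.

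**Working it through.** **1. The plan's own figure.** Inputs: difference 0.05, SD 0.06 (sections 4.A.2 and 12.E); alpha 0.05, taken as two-sided; power 80%.

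- Standardised difference: d = 0.05 / 0.06 = 0.833.
- n per arm = 2(1.960 + 0.842)² / 0.833² = 22.6, rounded up to 23.
- Two-sample t-test power: 78.9% at 23 per arm, 80.7% at 24.
- A one-sided calculation gives 18 per arm and does not match.

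So 23 per group is the sample size for a two-sided comparison of mean change.

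**2. What the chi-square test needs at 23 per arm.** Power was obtained by enumerating all 2×2 tables with 23 children per arm, using the uncorrected Pearson test at two-sided 0.05. This step needs no mean, SD or normality assumption. The table gives the true FC proportion required for 80% power.

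| SC proportion reducing | FC proportion needed | Gap (points) |
|---|---|---|
| 20% | 59% | 39 |
| 30% | 70% | 40 |
| 40% | 79% | 39 |
| 50% | 87% | 37 |
| 60% | 93% | 33 |
| 70% | 97% | 27 |

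If Fisher's test replaces chi-square whenever an expected count is below 5, the last two FC values become 94% and 99%. That trigger is an assumption, since the plan states none. The documents give no response proportions to set against this table.

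**3. Illustration only.** To link the two scales, assume normally distributed change, any decrease counted as reducing, a mean difference of 0.05 and an FC SD of 0.06. With SC mean change m and SC standard deviation s:

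- P(reduce, SC) = Φ(−m / s)
- P(reduce, FC) = Φ(−(m − 0.05) / 0.06)

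For m = 0 these are Φ(0) = 50.0% and Φ(0.833) = 79.8%. The power of the plain chi-square test at 23 per arm is:

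| SC mean change | SC SD 0.04 | SC SD 0.06 | SC SD 0.08 |
|---|---|---|---|
| +0.05 | 87% | 57% | 38% |
| +0.025 | 80% | 62% | 51% |
| 0 | 57% | 57% | 57% |
| −0.025 | 30% | 50% | 61% |
| −0.05 | 8% | 37% | 58% |

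With the Fisher fallback and SC SD 0.06, the values for −0.025 and −0.05 fall to 47% and 25%. The SC mean, the SC SD, normality, the definition of reducing and the Fisher trigger are all absent from the documents. The spread from 8% to 87% shows that no single power figure can be assigned to the chi-square test.

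**The case against.** The best counter-argument is that there is only one declared primary. The 12.B sentence is the only place where the words primary outcome are attached to a statistical test, and it agrees with the Aim 2 hypothesis. The Table 1 entry in 12.E names a variable, and a proportion reducing BMI z-score is still a BMI z-score outcome. The mixed model is never called primary; its coefficient is described as being of interest within that model. On this reading the model is a further analysis of unstated status. Figure 3 and the Table 2 cited in 12.E might also have clarified the matter: the figure is not reproduced and no table carries that label, so absence can be asserted only for the available text.

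The Table 1 label is indeed ambiguous on its own. But the 12.E analysis text specifies a continuous dependent variable, treats other measures as additional, and omits the proportion altogether. Even on the charitable reading, the model's status is undeclared and the power statement does not belong to the chi-square test.

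It is also fair that the aim is feasibility and preliminary effectiveness. The decision on further testing draws on RE-AIM dimensions, cost and acceptability, with no stated p-value threshold, so a false negative costs less than in a confirmatory trial. The sample-size basis is disclosed. This limits the consequence. It does not excuse a stated primary outcome, alpha and power that do not refer to one analysis.

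Finally, the illustration depends on outside assumptions, and some of its scenarios reach or exceed 80%. That stands: it cannot show that the chi-square test is underpowered, only that its power is unknown.

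**Conclusion.** The concern holds. Sections 12.B and 12.E specify different analyses of child BMI z-score as the main efficacy comparison, and no available text ranks them. The stated 80% power is correct to rounding for mean change (0.05, SD 0.06, two-sided) and has no stated basis for the chi-square test. For that test, 23 per arm gives 80% power only with true gaps of about 27 to 40 points under plain chi-square, across SC proportions of 20% to 70%. The contradiction and the misplaced power figure rest on the text alone. Only the normal-model illustration needs assumptions from outside the documents. This must be fixed before outcome data are analysed, because until then the primary result is undefined.

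**What to change.** Name one primary analysis and state it identically in 12.B, in 12.E Table 1 and in the 12.E Statistical Analysis. Label the other secondary, and attach the power statement to the one chosen. Either option below resolves the conflict.

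- **Option A, which fits the existing sample-size basis.** Make the 6-month between-group difference in mean child BMI z-score, adjusted for baseline, the primary analysis. Use ANCOVA or the 6-month contrast from the mixed model, and state the time point, because the present model text does not tie its group coefficient to one. Report the proportion reducing as secondary, with an odds ratio or risk difference and 95% CI.
- **Option B, which keeps the 12.B wording and the Aim 2 hypothesis.** Keep the proportion as primary. Define what counts as reducing and when Fisher's test replaces chi-square. Label the mixed model secondary. Replace the 80% figure with the investigators' own power calculation for that test at 23 evaluable per arm, stating the assumed proportions.

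The cost is a wording change in 12.B and 12.E, plus one new power calculation under Option B. No participants or measurements are added. The downside is that under Option A the proportion loses primary status, and under Option B the present 80% can no longer be claimed without its own justification and may turn out lower.
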